**Table 1. Eligibility Screening and Baseline Assessment Measures**

Instrument	Purpose	BSL	Exit	Daily
Breathalyzer Test	Screen for alcohol	X		
Urine Drug Test	Screen for drug use	X		
Pregnancy Test	Screen for pregnancy	X		
Breathalyzer Policy	Required document	X		
Participant Locator Form	Required document	X	X	
Participant Contact Form	Collect contact information	X		
Demographics Form	Collect demographics	X		
Participant History Form	Collect medical history and medications	X		
Adverse Events Form	Collect adverse Events		X	
EMA Morning Report	Collect daily substance use, partner conflict, mood and affect, device accessibility			X
EMA Random Report	Collect daily substance use, partner conflict, mood and affect, device accessibility			X
CIWA-Ar	Assess alcohol withdraw	X		
Mini Mental Status Exam (MMSE) 	Screen for cognitive deficits	X		
QuickSCID 	DSM-5 psychiatric disorders	X		
Traumatic Life Events Questionnaire (TLEQ) 	Assess trauma history	X		
Time Line Follow-Back 	Alcohol and drug use, IPV	X	X	
PTSD Checklist (PCL-5) 	Assess PTSD symptoms	X		
Beck Depression Inventory-II (BDI-II) 	Assess depression	X		
Alcohol Use Disorders Identification Test 	Alcohol problem severity	X		
Fagerstrom Test for Nicotine Dependence (FTND) 	Assess nicotine use	X		
Comprehensive Effects of Alcohol Questionnaire 	Alcohol expectancies	X		
Drinking Motives Questionnaire-Revised 	Drinking motives	X		
Revised Conflict Tactics Scale 	Intimate partner violence	X	X	
Dyadic Adjustment Scale-short form 	Relationship functioning	X	X	
State-Trait Anger Expression Inventory 	Trait anger	X		
Dissipation-Rumination Scale 	Hostile rumination	X		
Difficulties in Emotion Regulation Scale (DERS)	Assess Emotion Regulation	X		
Urgency, Premeditation, Perseverance, Sensation Seeking, Positive Urgency Impulsive Behavior Scale (UPPS-P)	Measure impulsivity	X		

HRV4Biofeedback Survey	Measure emotional state before and after breathing exercise during last 7 days			X
Breathing Prompt	Prompt breathing exercise during last 7 days			X
Website Analysis and Measurement Inventory 	Feasibility and Acceptability		X	
Post-Study System Usability Questionnaire 	Usability		X	
Client Satisfaction Questionnaire 	Client satisfaction		X	

**EMA Procedures.** Participants will download an application (provided by Illumivu, Inc.) on their mobile device. We will loan a compatible device and charger to participants who do not own one. Participants will complete a demo session (in person or via Doxy.me) with research staff to learn how to use the mobile device and EMA app and troubleshoot any challenges that arise. Four daily EMA reports will be requested via phone notification (Days 1-28; one morning report plus three subsequent reports at random times over the following 12 hours; i.e., one assessment per 4 hour time block). Participants will have the ability to select the time they receive the morning assessment and provide a daily window for start and end times. Both partners within each dyad will be assigned to the same assessment schedule. Participants will have 2 hours to complete the morning report and 30 minutes to complete subsequent reports, allowing flexibility to make up missed reports. Participants will also be instructed to complete event-driven reports if alcohol use or partner conflict occurs. Reports will include drinking and drug use, self and partner conflict behaviors, and subjective mood and affect. Research staff will contact participants by phone or text if the first two EMA entries on any particular day are missed.

**Physiological Assessment and Geolocation.** Participants will be issued a Garmin Vivosmart 4 activity tracker and charger and instructed to wear it continuously for 28 days of participation. We will instruct participants to charge the device during sleep to minimize disruption in data collection (60-90 minutes). No participant action is needed to store data from the tracker. EMA data is fully integrated with physiological data and geolocation using Illumivu's cloud-based server. This procedure will allow us to establish temporal sequence and both acute and lagged associations between HRV, drinking, and IPV, and to contextualize findings with geolocation. HRV measurements will be mean-centered for each participant in order to account for participants' baseline ("state"). *Illumivu, Inc. will provide cleaned data and peak, low, and average HRV for each 4-hour EMA assessment period.*

**HRV-B Implementation.** Participants will be trained at baseline and then will be randomly prompted once daily on days 22-28 to complete 10 minutes of HRV-B according to published protocol. Participants will also be able to use HRV-B more often if they choose. HRV-B will guide participants in an evidence-based paced breathing technique (about 6 breaths per minute) using visualization on their mobile device of their real-time cardiac parameters. This process can reduce sympathetic dominance, enhance autonomic stability, and affect regulation, which cannot be accomplished by alternatives such as relaxation or deep breathing because participants must learn to breathe at their individualized cardiovascular resonant frequency.

**HRV-B Usability, Feasibility, and Acceptability.** We will assess the number of started, incomplete, and completed HRV-B sessions. Participants will be prompted twice at random intervals to respond to a brief survey assessing HRV-B: 1) ease of use, 2) willingness to continue use, 3) perceived helpfulness, 4) patient satisfaction, and 5) suggestions for modifications. In addition to providing subjective usability, feasibility, and acceptability at the exit interview, participants will complete the Website Analysis and Measurement Inventory (WAMMI), Post-Study System Usability Questionnaire (PSSUQ), and 8-item Client Satisfaction Questionnaire (CSQ). The investigators will discuss these outcomes and integrate participant suggestions for our planned R01 application.

**Compensation.** Participants will receive \$50 for the baseline assessment, \$1 per completed EMA report (\$112 maximum), a \$10 bonus for each week in which ≥80% of EMA reports are completed (\$40 maximum), \$10 for the purchase of the HRV4Biofeedback app, \$25 for completing all 4 weeks of participation, and \$25 for returning borrowed equipment (*return mailers provided*) for a possible \$252 total. Participants will be compensated via Clincard, or with check or cash.

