**Strengths and Limitations of Design.** The long-term goal of this research is to enable the use of wearable technology to identify times of increased risk for alcohol-facilitated IPV due to physiological and emotional over-arousal, and to prepare for an R01 application proposing a randomized controlled trial of HRV-B delivered in a "just-in-time" fashion. These rich multimodal data will establish mechanistic testing procedures and explore patient-specific algorithms predicting optimal HRV-B engagement. Findings will make an essential scientific contribution and will optimize statistical power, HRV-B dose and timing, and participant preferences for our planned R01. This project will be the first to employ unobtrusive wearable technology and geolocation in a study of alcohol-facilitated IPV. A design allowing remote participation is a crucial scientific advancement. Although we will prioritize the analyses above to inform our R01 application, several alternatives were considered. We are equipped to examine additional physiological outcomes, time course of HRV recovery, lagged temporal ordering, and numerous individual, dyadic, and contextual differences in these outcomes. *It is possible that responding to EMA and feasibility/acceptability queries might influence HRV, drinking, or IPV outcomes during the assessment-only or HRV-B period. We have included exploratory analyses to specifically address this possibility and inform future clinical trial design.* The proposed HRV-B dose and timing was selected to provide preliminary data about when, where, and why participants elect to use HRV-B. The primary goal of this project is mechanistic, and intensive prompting or incentivizing HRV-B might confound outcomes. We are equipped to adjust implementation according to data-driven findings in our planned collaborative R01 application.

**Summary:** This project will use state of the art wearable technology and a novel combination of ecological momentary assessment, continuous physiological monitoring, and geolocation in a micro-longitudinal design. This unique approach, which has never been applied to alcohol-facilitated IPV, will advance the science in this area, elucidate the mechanistic role of HRV in alcohol-facilitated IPV in naturalistic settings, and position the study team to translate findings into a rigorous clinical trial design to mitigate alcohol-facilitated IPV.

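### From day 22 the 4-hour HRV summaries include the HRV-B sessions themselves, so HRV comparisons that use that week partly measure the exercise, mainly through peak HRV

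*Combined protocol and SAP*

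**What the plan says.** Under Physiological Assessment and Geolocation, participants get a tracker and are "instructed to wear it continuously for 28 days of participation". Storage is automatic: "No participant action is needed to store data from the tracker". The vendor "will provide cleaned data and peak, low, and average HRV for each 4-hour EMA assessment period". Cleaning is not defined, and each participant's HRV is centred on their own mean.

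Under HRV-B Implementation, participants are "randomly prompted once daily on days 22-28 to complete 10 minutes of HRV-B". Sessions are not capped: "Participants will also be able to use HRV-B more often if they choose". The exercise is paced breathing at about six breaths a minute. The training manual it follows, listed in the References, names greater cardiac variability as its aim.

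Under Strengths and Limitations of Design, the plan accepts that answering EMA and feasibility queries "might influence HRV, drinking, or IPV outcomes during the assessment-only or HRV-B period" and says that exploratory analyses address this. It gives no model and does not say which HRV summary they use. The main Aim 1 hypothesis is a different contrast: HRV in episodes with alcohol use and IPV against episodes with neither.

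**The concern.** On days 1-21 a block's peak, low and average describe spontaneous HRV. On days 22-28 the same variables also cover minutes in which the participant performs an exercise meant to raise HRV. The variable keeps its name and changes its meaning on day 22.

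Two uses are exposed. In a comparison of periods, the session minutes can be mistaken for reactivity to assessment, or for a benefit of HRV-B that lasts beyond the session. In the event contrast, the result depends on where sessions fall. Sessions concentrated in calm blocks raise non-event HRV and favour the hypothesis of lower HRV in event blocks; sessions concentrated around conflict or drinking hide it. Prompts are random, but extra sessions are the participant's choice.

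Timing matters too. A block maximum cannot be corrected once only the summary has been delivered.

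**Working it through.** **Inputs from the documents.** "Four daily EMA reports will be requested via phone notification" for 28 days; 4-hour (240-minute) periods; one prompted 10-minute session a day for 7 days.

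**Inputs assumed, because the documents give none.** In-session HRV of 1.25 to 3 times usual for the average, or session epochs raised by 1 to 3 within-block SD for the peak; epochs of 5 or 10 minutes, independent and normal; every prompted session done with the tracker on.

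**The plan's own count.** 4 × 28 = 112 reports, which matches the stated maximum payment of $112 at $1 each.

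**Exposure at one session a day.**
- Share of an affected block: 10/240 = 4.2%.
- Share of the days 22-28 blocks: 7/28 = 25%. Two sessions a day in separate blocks give 14/28 = 50%.
- Share of all blocks: 7/112 = 6.3%.

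The schedule can also be read as three 4-hour blocks a day. The shares are then 7/21 = 33% and 7/84 = 8.3%, and the weekly shifts below grow by a factor of 4/3.

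**Average HRV.** If in-session HRV is k times usual, an affected block's average rises by (k − 1) × 10/240, and the week's average by that × 7/28.

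| k | affected block | week |
|---|---|---|
| 1.25 | 1.0% | 0.26% |
| 1.5 | 2.1% | 0.52% |
| 2 | 4.2% | 1.0% |
| 3 | 8.3% | 2.1% |

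**Peak HRV.** 100,000 blocks were simulated, with 48 epochs of 5 minutes (two in session) or 24 epochs of 10 minutes (one in session). The rise in the block maximum is divided by the SD of the block maximum (0.468 and 0.509), then multiplied by 0.25 for the week.

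| session epochs raised by | affected block (5 min; 10 min) | week (5 min; 10 min) | session supplies the peak |
|---|---|---|---|
| 1 SD | 0.122/0.468 = 0.26; 0.108/0.509 = 0.21 | 0.07; 0.05 | 24%; 20% |
| 2 SD | 0.560/0.468 = 1.20; 0.465/0.509 = 0.91 | 0.30; 0.23 | 64%; 53% |
| 3 SD | 1.365/0.468 = 2.92; 1.157/0.509 = 2.27 | 0.73; 0.57 | 92%; 83% |

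By chance the session would supply the peak in 2/48 = 1/24 = 4% of blocks.

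**Low HRV.** The shift is 0.015 to 0.018 within-block SD, which is negligible.

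**Centring.** Subtracting one mean c per participant leaves the period difference unchanged: (A − c) − (B − c) = A − B.

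**Event contrast.** The bias in average HRV is (p1 − p0) × the affected-block shift, where p1 and p0 are the shares of event and non-event blocks that hold a session. It vanishes if the shares are equal. If all sessions fell in non-event blocks, and those were nearly all of the 112, it would be about 6.25% × (1.0% to 8.3%) = 0.07% to 0.5%. Clustering on the scarcer event blocks would weigh more, and the documents do not allow that to be bounded.

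**The case against.** The strongest reply is that little of the main analysis is exposed. Aim 1 compares event with non-event episodes, Aim 2 concerns usability, feasibility and acceptability, and no test of the HRV-B week against earlier weeks is laid out. The period analyses are exploratory, and the text on them concerns reactivity to queries. About 94% of blocks hold no prompted session, and the average moves little. The plan is silent rather than explicit about keeping session minutes, and undefined cleaning might remove them. All of this stands and limits the size of the point. It does not remove it: followed as written, the plan summarises every 4-hour period whole, peak is one of only three summaries, and which one is analysed is not stated.

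Three stronger readings are tempting but not supported.
- **Mood shifts by construction as well.** Table 1 lists an HRV4Biofeedback Survey ("Measure emotional state before and after breathing exercise during last 7 days"), but as an instrument separate from the EMA reports. Nothing pools the two, and mood is not among the outcomes named for the two periods.
- **The extra contacts in the last week are part of the same fault.** They bear on burden and reactivity, which the plan already acknowledges, and not on what the HRV summaries contain.
- **The artefact equals the d = 0.3 the study is sized for.** That d is a within-subject paired difference. The shifts here are scaled by other SDs, and for average HRV a value of 0.3 arises only in a single session block, at an assumed threefold rise and an assumed between-block SD.

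**Conclusion.** The point holds for HRV. On days 22-28 the block summaries contain the exercise, with no stated exclusion. A period comparison of peak HRV could be materially distorted, by about 0.05 to 0.7 SD of the block peak over the week. For average HRV the distortion is small, about 0.3% to 2% at one session a day, and for low HRV it is practically nil. The event contrast is affected less, through about 6% of blocks, and only if sessions are unevenly spread between event and non-event blocks.

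The exposure shares come from the plan's schedule. The effect sizes rest on the assumed in-session rise, epoch length and independence of epochs, and should be read as a range. The matter is worth correcting before the summaries are produced; it does not undermine the study's main aims.

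**What to change.** Specify that HRV-B session minutes, plus a short fixed margin after each session, are removed before peak, low and average HRV are computed. Report in-session HRV separately as a check that the exercise was delivered. Name the HRV summary used in any comparison between periods.

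This needs session start and stop times to reach whoever computes the summaries. The plan commits to counting sessions but does not say that their times are passed on. The before and after survey in Table 1 could locate sessions approximately if it is time-stamped, which the documents do not confirm. If exact times are not available, either exclude whole blocks known to contain a session, or repeat the event contrast on days 1-21 as a sensitivity analysis.

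The main option costs about 4% of the minutes in session blocks plus the margin, and the data transfer. Excluding blocks costs about a quarter of the days 22-28 blocks at one session a day; because extra sessions are self-chosen, those blocks may not be typical, so this is second best. The days 1-21 analysis sets aside 28 of 112 blocks (25%). With session minutes removed, their direct contribution is zero, and any remaining HRV difference between periods reflects carry-over, time trend or reactivity.

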## STATISTICAL ANALYSES.

**General.** All data will be collected in a REDCap database to ensure accuracy and validity and analyzed using SAS v9.4 (Cary, NC). Descriptive and summary statistics will characterize the sample and outcomes.

**Power and Sample Size.** Based on our enriched recruitment plan of couples with current AUD and IPV, and EMA studies of both healthy community couples and participants with IPV, we expect  $\geq 50\%$  of the couples enrolled in this study to report psychological or physical IPV during the 28-day study timeframe. Within-couple correlation of variables (HRV, alcohol use, IPV) will result in an effective sample size between  $N=50$  (the number of couples) and  $N=100$  (the number of individual participants). For example, for a within-couple intraclass correlation coefficient (ICC) of 0.1 or 0.3, sample sizes approximate  $N=90$  and  $N=76$ , respectively. At a minimum, the planned sample size conservatively provides 80% power to detect within-subject differences in HRV equivalent to Cohen's  $d$  effect sizes of 0.3 (the detectable difference with 1 paired set of observations on the  $\geq 50\%$  of subjects expected to report alcohol use and IPV), consistent with those observed in our preliminary studies (see Figure 1). However, given the volume of EMA data collected and despite the fact that many EMA reports will not involve alcohol or IPV, we may even be able to detect much smaller differences. For comparisons between partners within a dyad, we anticipate that effect sizes as small as 0.4 and correlations as small as 0.4 will be detectable with 80% power. Having  $N=100$  participants will also provide 85% power to detect whether feasibility and acceptability metrics are lower than 80%. These power analyses assume 2-sided testing and an alpha level of 0.05.

**Strengths and Limitations of Design.** The long-term goal of this research is to enable the use of wearable technology to identify times of increased risk for alcohol-facilitated IPV due to physiological and emotional over-arousal, and to prepare for an R01 application proposing a randomized controlled trial of HRV-B delivered in a "just-in-time" fashion. These rich multimodal data will establish mechanistic testing procedures and explore patient-specific algorithms predicting optimal HRV-B engagement. Findings will make an essential scientific contribution and will optimize statistical power, HRV-B dose and timing, and participant preferences for our planned R01. This project will be the first to employ unobtrusive wearable technology and geolocation in a study of alcohol-facilitated IPV. A design allowing remote participation is a crucial scientific advancement. Although we will prioritize the analyses above to inform our R01 application, several alternatives were considered. We are equipped to examine additional physiological outcomes, time course of HRV recovery, lagged temporal ordering, and numerous individual, dyadic, and contextual differences in these outcomes. *It is possible that responding to EMA and feasibility/acceptability queries might influence HRV, drinking, or IPV outcomes during the assessment-only or HRV-B period. We have included exploratory analyses to specifically address this possibility and inform future clinical trial design.* The proposed HRV-B dose and timing was selected to provide preliminary data about when, where, and why participants elect to use HRV-B. The primary goal of this project is mechanistic, and intensive prompting or incentivizing HRV-B might confound outcomes. We are equipped to adjust implementation according to data-driven findings in our planned collaborative R01 application.

**Summary:** This project will use state of the art wearable technology and a novel combination of ecological momentary assessment, continuous physiological monitoring, and geolocation in a micro-longitudinal design. This unique approach, which has never been applied to alcohol-facilitated IPV, will advance the science in this area, elucidate the mechanistic role of HRV in alcohol-facilitated IPV in naturalistic settings, and position the study team to translate findings into a rigorous clinical trial design to mitigate alcohol-facilitated IPV.

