**Specific Aim 2:** Conduct a non-randomized, open-label pilot study examining the usability, feasibility, and acceptability of a remote heart rate variability biofeedback (HRV-B) intervention to reduce alcohol-facilitated IPV.

We hypothesize that episodes of alcohol use and IPV will be characterized by lower HRV as compared to episodes when neither alcohol use nor IPV occurs. We also hypothesize that HRV-B will demonstrate usability, feasibility, and acceptability as evidenced by use at least once daily and positive self-reported feedback. This translational study will advance the mechanistic science in this area by examining the proximal role of HRV in alcohol-facilitated IPV in naturalistic settings. This study has the added benefit of utilizing discreet wearable technology and geolocation to refine and optimize the content, dose, and timing of HRV-B. Findings will facilitate

the development of urgently needed just-in-time interventions that are personalized, accessible, and dynamic. The investigative team has the unique expertise necessary to implement this innovative study, which has the potential to yield essential public health impact. Findings will directly inform the design of a randomized controlled trial testing the efficacy of HRV-B to reduce alcohol-facilitated IPV through R01 series funding.

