### **A. Human Subjects Involvement, Characteristics, and Design**

A total of 50 couples (100 individual participants) between the ages of 21 and 70 will be recruited over a 2-year period. Women and members of minority groups will be eligible for participation and we will strive to enroll an equal number of women and men with AUD. Children ages 18-21 are *not* eligible for participation. Study inclusion/exclusion criteria are as follows:

Inclusion criteria

- 1) Any gender identity; any race or ethnicity; any sexual orientation; aged 21-70 years.
- 2) Married, cohabiting, or in a committed relationship for  $\geq 6$  months.
- 3) English fluency and cognitive functioning sufficient to provide informed consent and participate accurately (score  $\geq 26$  on the Mini-Mental Status Exam [MMSE]).
- 4) At least one partner within each dyad must meet DSM-V diagnostic criteria for current AUD (assessed by the QuickSCID) *and* current alcohol use based on TLFB.
- 5) At least one partner within each dyad must endorse  $\geq 1$  instance of IPV with their current partner in the past two years (assessed by the Revised Conflict Tactics Scale [CTS-2]).
- 6) Maintenance of psychotropic medications on a stable dose for at least 4 weeks before study initiation.

Exclusion criteria:

- 1) Meeting DSM-5 criteria for a history of or current psychotic, bipolar, or antisocial personality disorders.
- 2) Meeting DSM-5 diagnostic criteria for moderate or severe drug use disorder (e.g., cannabis). Concurrent mild drug use disorders are acceptable due to the marked co-occurrence in AUD populations. Moderate or severe Nonalcoholic Substance Use Disorder is acceptable if there has been no current substance use in the last 1-2 months.
- 3) Alcohol withdrawal as indicated by CIWA-Ar scores  $>8$ .
- 4) Current suicidal or homicidal ideation and intent.
- 5) Serious cardiovascular health conditions (e.g., pacemaker, cardiac arrhythmia, hypertension) *because the safety of HRV-B has not yet been established in these populations.*
- 6) Treatment on medications such as lithium, methadone, alpha or beta blockers or cholinergic/ anticholinergic medications likely to confound normative cardiovascular responding.
- 7) Current neurologic conditions or history of traumatic brain injury.
- 8) Severe *and* unilateral IPV in the past 6 months.
- 9) Current pregnancy.

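### The power paragraph moves from half of couples with any IPV to half of subjects with alcohol use and IPV, and the detectable d of 0.3 follows from neither

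*Combined protocol and SAP*

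**What the plan says.** All the power statements stand in one paragraph, Power and Sample Size, under STATISTICAL ANALYSES.

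- **First rate.** Citing enriched recruitment and earlier EMA studies, the plan expects at least 50% "of the couples enrolled in this study to report psychological or physical IPV during the 28-day study timeframe". The unit is the couple, and alcohol is not part of the event.
- **Second rate.** Three sentences later the detectable difference is tied to at least 50% "of subjects expected to report alcohol use and IPV". The unit is now the individual, and the event requires both alcohol use and IPV.
- **Detectable difference.** The planned sample "conservatively provides 80% power to detect within-subject differences in HRV" for "effect sizes of 0.3 (the detectable difference with 1 paired set of observations on the" second rate just quoted. The scale is Cohen's d. The paragraph closes: "These power analyses assume 2-sided testing and an alpha level of 0.05".
- **Clustering.** Within-couple ICCs of 0.1 and 0.3 are said to leave effective samples of about 90 and 76.

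The hypothesis under SPECIFIC AIMS is that "episodes of alcohol use and IPV will be characterized by lower HRV as compared to episodes when neither alcohol use nor IPV occurs". Of the EMA reports, EMA Procedures says: "Reports will include drinking and drug use, self and partner conflict behaviors, and subjective mood and affect". The inclusion criteria (Human Subjects Involvement, Characteristics, and Design) require AUD with current drinking in only one partner, and ask only one partner to endorse past IPV.

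**The concern.** The first rate does not imply the second. Getting from 25 couples with any IPV to 50 individuals with a joint event requires that every one of those couples has an alcohol-linked episode and that both partners count toward it. The plan states neither condition. Eligibility does not supply them either, because one partner may not be a drinker and IPV can occur without alcohol.

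The power claim depends on how many people can supply a pair of HRV values. If that number is smaller than assumed, or if d = 0.3 was not computed from it, the figure offered as a conservative minimum is too favorable. The project is meant to inform the design of a later randomized trial, so an optimistic figure would carry forward.

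A secondary point concerns roles. HRV is measured per person, but the text does not say whose drinking defines an index episode, or whether the IPV is perpetrated or received. Without a rule, the HRV of a sober recipient could be averaged with that of an intoxicated aggressor, and the two effects could not be told apart afterwards.

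**Working it through.** **Inputs from the plan:** 50 couples, 100 individuals; at least 50% with an event; one pair per subject; two-sided alpha 0.05; 80% power; d = 0.3; ICC 0.1 or 0.3.

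**1. The plan's effective sample sizes.** With two members per couple, effective N = 100/(1 + ICC).
- ICC 0.1: 100/1.1 = 90.9 (plan: 90).
- ICC 0.3: 100/1.3 = 76.9 (plan: 76).

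These reproduce, apart from rounding down.

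**2. Pairs needed for d = 0.3.** Normal approximation: n = ((1.960 + 0.842)/0.3)² = 87.2, so 88. The exact noncentral t calculation gives 90. One-sided, the exact figure is 71. The stated basis of 50 subjects reaches neither.

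**3. Detectable d on each basis** (paired t, exact, two-sided 0.05, 80% power):

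| Contributing subjects | n | Detectable d | Power for d = 0.3 |
|---|---|---|---|
| 50% of 100 individuals, no clustering | 50 | 0.40 | 55% |
| Same, ICC 0.1 (half of 90) | 45 | 0.43 | 50% |
| Same, ICC 0.3 (half of 76) | 38 | 0.47 | 44% |
| One partner in each of 25 couples | 25 | 0.58 | 30% |

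The ICC rows assume that the plan's ICC applies to the paired HRV difference.

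**4. What would give 0.3.**
- At n = 90 the detectable d is 0.299 and power for 0.3 is 80.4%. That n equals the plan's effective sample for all 100 participants at ICC 0.1, not for half of them. At ICC 0.3, even all 100 participants (about 77 effective) give 0.32.
- If d is scaled by the raw SD, not the SD of the differences, then d = dz × √(2(1 − ρ)), where dz is the detectable value in step 3. At n = 50: ρ = 1 − (0.3/0.404)²/2 = 0.72. The required ρ is 0.75 at n = 45, 0.79 at n = 38 and 0.87 at n = 25. The plan gives no correlation.

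**5. From couples to subjects.** 50% of 50 couples is 25 couples. If both partners qualify in every one of them, 50 subjects contribute; if one partner qualifies in each, 25 do. If only some IPV couples have an alcohol-linked episode, the number falls further. The plan gives no such share, so I put no figure on that case.

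**The case against.** Several points on the other side have force.

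- **The contrast itself is stable.** A reader might infer that the Aim 1 event is redefined partway through the plan. It is not: SPECIFIC AIMS states one contrast, joint episodes against episodes with neither. Only the expected proportion in the power paragraph shifts.
- **Couples to subjects is partly defensible for IPV.** EMA asks about own and partner conflict behavior, so both members can report the same episode. This supports the step from couples to individuals. It does not supply the alcohol condition.
- **One pair is labeled a minimum.** Each person has up to 112 scheduled reports (4 × 28), and the plan says smaller differences may be detectable. That may be so, but the gain is not quantified, and 0.3 is presented as what one pair already delivers.
- **Pooling of roles is not planned.** A reader might infer that aggressor and recipient HRV will be merged. The text permits this by silence only. It collects self and partner behavior, powers contrasts between the two partners, and lists dyadic differences among possible analyses. Severe and unilateral recent IPV is also excluded, though that does not rule out one-sided episodes during the study.
- **An aggressor-only event is not the only reading.** Aim 1 concerns couples, and discarding received-only episodes would lose scarce data.
- **The text may be condensed.** Strengths and Limitations of Design refers to analyses above, but no Aim 1 model appears, and Figure 1 is not available. The scale of the preliminary effect sizes cannot be checked.

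The missing link between the two rates and the arithmetic behind 0.3 remain unanswered.

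**Conclusion.** The plan should correct this, but it does not invalidate a proof-of-concept pilot. On the plan's most favorable reading, 50 independent subjects with one pair each, the detectable d is 0.40 and power for 0.3 is 55%. The plan's own ICCs raise the detectable value to 0.43 to 0.47. With one qualifying partner in each of 25 couples it is 0.58, with power 30%. These figures assume a paired t-test, d scaled by the SD of the differences, one pair per subject and no missing data. A stated raw-SD scale with ρ near 0.72 would rescue 0.3 at n = 50 without clustering.

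Three stronger conclusions are tempting but unsupported.
- That only a dozen or so subjects will contribute: this rests on an assumed alcohol share that the plan does not give.
- That pooling roles halves the effect: this requires no recipient effect, one-sided episodes and equal weighting. Recipients could equally add to the signal.
- That the figure was computed on the whole sample by mistake: 0.3 matches n = 90, but the plan does not show how it was obtained.

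**What to change.** **In Power and Sample Size:**
1. Restate the one-pair detectable difference as about 0.40 to 0.58 for 50 down to 25 contributing subjects. Note that clustering moves the upper-n end to 0.43 to 0.47, and that the difference grows if only some IPV couples have alcohol-linked episodes. Alternatively, keep 0.3 and state the scale of d and the within-person correlation that support it.
2. Label the proportion of subjects with a joint event as an assumption, distinct from the couple-level IPV rate, and say how many partners per couple are taken to qualify.
3. If repeated EMA observations are relied on for more power, give the assumed number of events per person and the resulting figure.

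**Secondary, before analysis:** code each person-period by own and partner drinking and by perpetrated and received IPV. The plan's self and partner wording covers conflict behavior, so partner drinking may need linking from the partner's own reports. State the time window joining drinking to IPV. Include role as a term in a within-person dyadic model, with partners nested in couples, so that aggressor and recipient effects can be reported separately and received-only episodes are kept.

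**Cost:** a less favorable stated detectable difference, revised wording and one derived variable. No new data collection is needed.
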